In short, the study is a superiority trial that aimed to randomise at least 96 individuals with social anxiety-disorder to one of two 12-week group treatments for SAD (IE-GCBT and VB-GCBT). There is also a one-month follow up group review session. Over 20 outcome measures have been collected at various times before, during, and after treatment. The primary endpoint is the one month follow up (i.e., coinciding with the follow up group review session). This was selected on the basis of pilot data which showed differences between the treatments are larger at one-month follow up than at the end of weekly treatment sessions (McEvoy et al., 2015). No interim analyses or stopping rules were planned, nor have any been used.

The primary hypotheses are that, at the one-month follow up, IE-GCBT will be superior to VB-GCBT in terms of (a) reduction in severity of self-reported social anxiety symptoms (b) percentage of individuals with a SAD diagnosis (c) reduction in clinician-rated severity of social anxiety symptoms. McEvoy et al. (2017) also describe a wide range of additional hypotheses concerning secondary outcome measures, mechanisms of change, and moderation. Given the numerous outcomes and possible research questions, it is not possible to comprehensively report them all in a single paper. Therefore, they will be addressed across several publications.

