We will now describe how each imputed dataset will be analysed. The choice of analytical approach was determined by both the type of measurement of the outcome (e.g., binary or continuous) and the number of repeated assessments (i.e., number times that these outcomes were measured). These attributes for the outcomes are summarised in Table 1. See the trial protocol paper for more information about outcomes in the trial and their measurement properties (McEvoy et al., 2017).

Table 1

Measurement Properties and Repeat Assessments for Outcomes under Analysis

Outcome	Type of Measurement	Number of Measurements	
		Baseline	Post-Baseline
Primary			
SIAS	Continuous	2	5
SCID-5 Diagnostic Status	Binary	1	2
Clinician Rated Severity	Ordinal (Ranges 0 – 8)	1	2
Secondary			
SPS	Continuous	1	5
BFNE-S	Continuous	1	13
FPE	Continuous	1	13
PROMIS Anxiety	Continuous	2	13
PROMIS Depression	Continuous	2	13

All outcomes aside from SCID-5 diagnostic status, clinician-rated severity, and reliable and clinically-significant change will be analysed using Linear Mixed Models (LMM), as implemented in the R package nlme (Pinheiro, Bates, DebRoy, Sarkar, & R Core Team, 2019). There are some aspects of these analyses that will be the same for all outcomes and some that will differ depending on the number of measurement times for each outcome. The analytical decisions that are the same for all outcomes will be described first, followed by separate sections detailing the decisions individual to each analysis. A summary of the analyses and parameterizations of each is presented at the end.

Accounting for Nesting Within Group

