A key concern with the analysis of ordinal data is whether there are sufficient numbers of individuals at each of the rating categories. If there are only a small number of

individuals within a given severity rating, the estimated relationships could be easily influenced by outlying, or simply unrepresentative, responses. This is likely to be the case for the largest and smallest ratings of severity. If severity categories have low numbers of endorsements (< 5), those categories will be collapsed.

It should be noted that the CLMM relies on the assumption of proportional odds. This assumption implies that the effect of the covariates (e.g., treatment) are the same for every category. In other words, regardless of whether the individual has a high or low severity rating, their probability of changing category after receiving treatment is the same. If this is not the case, the resulting estimates of treatment effect are likely to be biased. An alternative is to estimate a different effect for each category. While this is more flexible, and does not assume proportional odds, it also requires estimating more parameters. The analysis of clinician-rated severity will first be carried out assuming proportional odds. The proportional odds assumption will then be evaluated. If there is a substantial departure from proportional odds for a given covariate, the analysis will be refitted with non-proportional odds for that covariate.

Reliable and Clinically Significant Change (SIAS)

Beyond simply testing whether the amount of change in social anxiety symptoms is statistically significant, it is also of interest to examine whether those changes are: a) beyond what would be expected due to measurement error, and b) clinically meaningful. This is the examination of reliable and clinically significant change (RC and CSC, respectively) described by Jacobson and Truax (1991). The analyses will examine the RC and CSC of the SIAS using the multiply-imputed datasets.

The calculation of RC is defined as:

$$RC = \frac{(SIAS_{pos} - SIAS_{pre})}{\sqrt{2 * SE^2}}$$

Where:

$$SE = SD_{pre} * \sqrt{1 - r}$$

Where r is the reliability of the SIAS. For this analysis, the previously described McDonald's Omega coefficient will be used as the estimate of the reliability of the SIAS. If

$RC > 1.96$, this indicates that the amount of change is greater than can be attributed to measurement error.

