The criteria for having achieved CSC were the same as described in previous pilot research (McEvoy et al., 2015). Individuals were required to have scored above a severity cut-off before treatment, achieved RC, and subsequently scored below the cut-off after treatment. The severity cut-off was defined as the mid-point between the clinical and normative means reported by Carleton et al. (2014), which was 40.56 for the SIAS.

To determine whether the proportions of individuals achieving reliable and/or clinically significant change significantly differed between treatment arms, a pooled test of the difference in proportions was carried out (the same procedure described for the analysis of diagnostic status).

Contrasts for Continuous and Ordinal Outcomes

The primary hypotheses are concerned with whether there are differences between the treatments at one month follow up. In order to determine this, for each continuous and ordinal outcome, the data from all the measurement occasions are jointly modelled using a LMM (rather than say, only using the one-month follow-up data in the analysis; see Mallinckrodt and Lipkovich (2017)). We will then use contrast coefficients to (i) estimate the marginal means for each treatment at each measurement occasion, and (ii) compute the mean difference between treatments and a standard error at the one-month follow up time point. For continuous and ordinal outcomes, we will compute the contrasts using R's emmeans package. For the ordinal outcome this contrast is an odds ratio, representing the difference in probability of belonging to a higher severity rating between the two treatment arms.

Evolution of Outcomes Over Time

A secondary goal of this paper is to understand how differences between the groups evolve over time. Analyses of pilot data suggest these tend to be smaller at post-treatment than at one-month follow up. We have no pilot data for the six-month follow up. Therefore, we will use additional contrasts to examine differences between the treatments at week 12 (end of weekly treatment sessions) and the 6-month follow up. This will provide valuable information about the evolution of treatment outcomes before and after the primary endpoint.

Reporting of Results

Analysis Code and Output

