All analysis code and output will be uploaded to the Open Science Foundation. This will ensure that all results are replicable, and that other scholars can easily extend our work. In the paper itself, we will summarise the key findings.

Standardized Effect Size

For continuous outcomes, we will convert the mean difference between groups into a standardised effect size by dividing the difference by the pooled pre-treatment standard deviation. We will also compute standardized within-group effect sizes, by subtracting the mean baseline score from each treatment's estimated marginal mean at the one-month follow up and dividing by the pooled pre-treatment standard deviation. For binary outcomes, the difference in proportion is an effect size. For ordinal outcomes, the odds ratio is an effect size.

Confidence Intervals

For each outcome, we will report a 95% confidence interval for the difference between groups at one-month follow up.

P-values

There have recently been calls to reform or abandon significance testing (for more details, see a recent special issue of the American Statistical Association's *American Statistician* journal [here](#)). In the present paper, we will report p-values continuously (e.g., $p = .078$) rather than just reporting whether they are less than or greater than .05.

Multiplicity

Due to the moderate sample size, there is a greater risk of Type II errors than Type I errors in the current trial. All hypotheses are also prespecified and the number of outcomes being analysed is limited. Therefore, no adjustment for multiplicity will be used.

Diagnostic Checks, Sensitivity, and Alternative Analyses

Model Assumptions

The graphical 'lineup' procedure will be used to assess the model assumptions of residual normality and normality of random effects for the mixed-model analyses of continuous and

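### A failed proportional-odds check on treatment would replace the single severity odds ratio with one per threshold and leave primary hypothesis (c) without a defined test, which can raise the false-positive rate

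*SAP*

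**What the plan says.** Primary hypothesis (c) is superiority at one month on "c) reduction in clinician-rated severity of social anxiety symptoms" (SAP, Trial Design, Methods, and Selection of Outcomes). The measurement-properties table lists the scale as "Ordinal (Ranges 0 – 8", that is, nine possible ratings.

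The section on the ordinal outcome specifies a cumulative-link mixed model. Sparse ratings are merged: "If severity categories have low numbers of endorsements (< 5), those categories will be collapsed". The model is first fitted with proportional odds, and the assumption is then evaluated. The section gives treatment as its example of a covariate to which the assumption applies, and describes the alternative as a separate effect for each category. The rule reads: "If there is a substantial departure from proportional odds for a given covariate", then "the analysis will be refitted with non-proportional odds for that covariate". It names no test, cut-off or plot for deciding what is substantial.

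Other sections assume a single result:
- Contrasts for Continuous and Ordinal Outcomes: "For the ordinal outcome this contrast is an odds ratio".
- Standardized Effect Size: "For ordinal outcomes, the odds ratio is an effect size".
- Confidence Intervals: one 95% interval per outcome for the one-month group difference.
- Pooling Results: 100 estimates and 100 standard errors per outcome, combined by Rubin's Rules.

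The closing summary table gives no alternative for the refitted model.

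**The concern.** If treatment triggers the refit, the model no longer contains one treatment odds ratio at one month. It contains one for each cut between adjacent categories, and the SAP names no deciding threshold, joint test, average, or retained proportional-odds estimate. Hypothesis (c) then has no defined estimate, interval or p-value. The tipping-point analysis, which seeks the shift at which significance is lost, is undefined for this outcome too.

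The switch depends on the same data that supply the result, and its criterion is open. If a reader or author then took (c) as supported because some threshold had p<0.05, the error rate would exceed the nominal level.

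The refit is also unnecessary for a valid test. If treatment has no effect, every threshold odds ratio equals 1, so treatment odds are proportional and the common odds ratio remains a valid test of no effect. Non-proportionality matters for describing an effect that exists.

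**Working it through.** The SAP states no power or error rate for this outcome, so there is no figure to reproduce. The check asks what happens when the arms are identical.

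**Inputs from the SAP.** The trial "aimed to randomise at least 96 individuals", taken here as 48 per arm. Nine ratings give at most 9 − 1 = 8 thresholds; merging ratings with fewer than 5 endorsements leaves fewer.

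**Assumptions.** Two-sided 0.05, implied by the 95% intervals. The trigger is a likelihood-ratio test of proportional odds for treatment, at p<0.05 or p<0.20, because the SAP gives no criterion. The model uses the one-month time point only, without baseline severity, random effects or imputation. Category probabilities are equal or mildly uneven.

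**Crude ceiling.** If k threshold tests were independent, P(any p<0.05) = 1 − 0.95^k: 9.8% for k=2, 18.5% for k=4, 33.7% for k=8. Threshold odds ratios from the same patients are strongly correlated, so simulation is needed.

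**Two-stage procedure, any threshold counted.** Overall error = P(triggered and any threshold p<0.05) + P(not triggered and common odds ratio p<0.05). For five equal categories and trigger p<0.05, 5.60% of null trials trigger, 2.52% trigger and show a significant threshold, and 4.66% do not trigger but have a significant common odds ratio. The sum is 2.52 + 4.66 = 7.18%. Among triggered trials the share with a significant threshold is 2.52/5.60 = 45%.

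Results by number of categories left (5,000 to 6,000 null trials per setting):

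| Categories | Common odds ratio only | Always refit, any threshold | Two-stage, trigger p<0.05 | Two-stage, trigger p<0.20 |
|---|---|---|---|---|
| 3 | 5.4-5.6% | 8.5-8.8% | 6.7% | 9.0% |
| 4 | 5.2-5.3% | 12.5-12.6% | 7.4% | 10.7% |
| 5 | 5.1-5.4% | 13.3-14.7% | 7.2-8.1% | 10.8-11.3% |
| 6 | 5.0-5.1% | 16.2-17.3% | 7.3% | 12.3% |
| 7 | 5.1-5.5% | 17.0-17.4% | 8.6% | 12.3% |

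A separate run with about 8 categories left after collapsing (3,000 null trials) gave 8.3% at trigger p<0.05 and 12.0% at p<0.20, against 5.6% for the common odds ratio. Further runs gave values as low as about 6% and 9%.

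**Alternatives after the trigger.**
- Average log odds ratio over thresholds, fixed in advance: 4.5-5.8%.
- One threshold named in advance: about 5.1-6.7%.
- Joint test of all thresholds, used only after the trigger: 8.3-9.5%. Used unconditionally: 5.4-6.2%.

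A joint test brought in only when the check fails therefore does not restore 5%, because it is applied to trials selected for looking non-proportional.

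**The case against.** A reader might infer that the refit itself inflates false positives. The SAP does not support that. All the inflated two-stage figures in the table need a further step, counting whichever threshold is significant, and the SAP never says so. Its wording of one contrast and one interval points the other way. With a single averaged contrast kept after the refit, error stays near 5%.

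Nor do the most alarming figures carry over. The 33.7% ceiling assumes eight independent thresholds, whereas the SAP expects to merge sparse ratings. The chance of a significant threshold once the check has failed (33-53% across settings at p<0.05) applies only to the 5-7% of null trials that trigger. The p<0.20 results rest on an assumed cut-off.

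There are further mitigating points. The proportional-odds model is always fitted first, so its odds ratio will exist. Output is to be published, p-values are reported continuously, and the analyst is masked, which limits deliberate choice of a favourable threshold. The Multiplicity section argues from the number of outcomes and does not discuss several parameters within one model, so it should not be read as a ruling on adjustment across thresholds. The SAP also justifies the refit by bias in the estimated effect, which is a legitimate aim.

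These points reduce the likely harm. None says which estimate judges (c) after a treatment refit.

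**Conclusion.** The point holds as an internal conflict: a data-driven rule for a primary outcome can produce a result that does not fit the SAP's own one-month contrast, interval and pooling step, and it leaves (c) without a defined test. The false-positive consequence is possible rather than certain. If any significant threshold were counted, overall type I error would rise from about 5% to roughly 6-9% with a p<0.05 trigger and 9-12% with p<0.20. It stays near 5% if one contrast is fixed in advance. The figures rest on 48 per arm, assumed triggers and category spreads, and a model without baseline, random effects or imputation, so they show the order of magnitude only. The conflict in the text does not depend on them.

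**What to change.** In the section on the ordinal outcome, state that the common (proportional-odds) treatment odds ratio at one month, with its 95% CI, is the test of hypothesis (c) whatever the assumption check shows. If the check fails for treatment, report the threshold-specific treatment odds ratios descriptively beside it. Keep the non-proportional refit for nuisance covariates such as baseline severity, define what counts as a substantial departure, and say whether the check is made once or in each imputed dataset. A single average contrast over thresholds, fixed in advance, is an acceptable alternative if the authors want the refit to apply to treatment.

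The change is to SAP wording only. The downside is that under a truly non-proportional effect the common odds ratio is an average over thresholds, so it must be read together with the descriptive table.

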In the first paper, we will report measures related to the primary hypotheses and key secondary hypotheses (see Table 1). The first three outcomes (self-reported SAD severity, diagnostic status, and clinician-rated severity) were selected in order to test the primary hypotheses. The remaining measures were selected because we judged them to be the most important secondary outcomes. Fear of negative evaluation is a mechanism proposed to underly SAD, thus it is relevant to evaluate whether IE-GCBT is superior to VB-GCBT in changing this mechanism. Similarly, in the treatment clinic where the trial is being conducted, SAD is often comorbid with major depression and generalised anxiety disorder. Therefore, it is meaningful to evaluate whether the treatments differ in their impact on the severity of symptoms of these comorbid conditions. Additional research questions and outcomes (e.g., moderators and predictors of change, health economic outcomes, and psychophysiological parameters) will be reported in subsequent papers. The remainder of this SAP describes how the variables that will be reported in the main outcomes paper will be analysed.

Table 1

Outcomes to be Reporting in the First Paper

Construct	Measure
Primary Outcomes	
Severity of social interaction anxiety (self-report)	Social Interaction Anxiety Scale (SIAS)
Presence or absence of SAD diagnosis (clinician-rated)	SCID-5 SAD diagnostic status
Severity of SAD diagnosis (clinician-rated)	Clinician-rated severity scale
Secondary outcomes	
Severity of social performance anxiety	Social Phobia Scale (SPS)
Severity of fear of negative evaluation	Brief Fear of Negative Evaluation - Straightforwardly Worded (BFNE-S)
Severity of fear of positive evaluation	Fear of Positive Evaluation Scale (FPE)
Severity of general anxiety	PROMIS Anxiety - Form 8A
Severity of depression	PROMIS Depression - Form 8A
Reliable & clinically significant change in social interaction anxiety	SIAS (categorised in accord with Jacobson & Truax, 1991)

Planned Reporting of Patient Characteristics and Measures

CONSORT Flow Chart

We will include a CONSORT flow chart showing the number of participants:

- Screened for the study
- Assessed
- Randomised
- Starting treatment
- Providing follow-up data

The chart will also show the reasons (where known) why participants did not meet trial eligibility criteria, discontinued treatment, and so on.

Number of Sessions Completed

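### The reliable-change rule has the wrong sign: as written it flags only patients who got worse, and no patient can reach clinically significant change

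*SAP*

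**What the plan says.** Under the heading Reliable and Clinically Significant Change (SIAS), the SAP sets RC = (SIAS post − SIAS pre) / √(2·SE²), with SE = SD_pre·√(1 − r). For r, "McDonald's Omega coefficient will be used as the estimate of the reliability of the SIAS". The decision rule is "RC > 1.96$, this indicates that the amount of change is greater than can be attributed to measurement error".

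The CSC rule then builds on RC: "Individuals were required to have scored above a severity cut-off before treatment, achieved RC, and subsequently scored below the cut-off after treatment". The cut-off is the midpoint of a clinical and a normative mean, "which was 40.56 for the SIAS".

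Two other places fix the direction of benefit. The primary hypotheses in the trial design section speak of "reduction in severity of self-reported social anxiety symptoms", and the table of outcomes for the first paper lists the SIAS under "Severity of social interaction anxiety (self-report". A lower score is therefore better.

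The same table lists reliable and clinically significant change as a secondary outcome. The section ends with a pooled between-arm test of the proportions achieving reliable and/or clinically significant change.

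**The concern.** The numerator is post minus pre on a scale where a fall is a benefit, but the threshold is placed on the positive side only. The SAP has no absolute value, no branch for RC below −1.96, and no separate categories for improved and deteriorated patients.

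Coded as printed, the reliable-change comparison becomes a comparison of deterioration rates, labelled as achievement. The CSC comparison becomes 0% against 0%. An analyst who notices must choose a repair that was not prespecified. The two natural repairs do not give the same reliable-change proportion. The SAP says that it supersedes the analyses in the protocol paper and that it will be time-stamped and made public, so this text is the governing definition.

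**Working it through.** **Inputs from the SAP.** RC formula, threshold 1.96, CSC rule and cut-off 40.56, all from the reliable-change section. The SAP gives no value for SD_pre or for omega.

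**The plan's own figure.** 1.96 is the two-sided 5% normal critical value (1.95996). The number is fine; the fault is the side on which it is applied.

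**Sign of RC.** For any SD_pre > 0 and r < 1 the denominator is positive, so RC has the sign of post − pre.

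- RC > 1.96 ⇔ post − pre > 1.96·√2·SD_pre·√(1 − r) > 0. This is a rise in severity.
- CSC requires pre > 40.56 > post, hence post − pre < 0 and RC < 0.
- RC < 0 and RC > 1.96 cannot both hold. CSC is empty for every data set, in both arms.

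**Worked patients (assumed SD_pre = 12, r = 0.90).** Denominator = √(2 × 144 × 0.10) = √28.8 = 5.37.

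| Pre | Post | RC as written | Flagged? | Clinical direction |
|---|---|---|---|---|
| 55 | 35 | −20/5.37 = −3.73 | No | Improved, crosses the cut-off |
| 55 | 75 | +20/5.37 = +3.73 | Yes | Worsened |

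**Enumeration.** All integer pre/post pairs from 0 to 80 (assumed score range) were checked for SD_pre of 8, 10, 12, 14 and 16 with r of 0.80, 0.85, 0.90 and 0.95, which makes 20 combinations.

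- As written, 0 pairs reach CSC in every combination, and no pair with post ≤ pre is flagged as reliable change.
- With |RC| > 1.96, or with the numerator reversed, 1,450 to 1,630 pairs reach CSC, depending on SD_pre and r. The two repairs give the same CSC count in each combination.

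**Size under illustrative assumptions.** None of these values is in the SAP: baseline mean 50, SD 12; mean change −12, SD of change 12, normal; r = 0.92.

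- Denominator = 12 × √(2 × 0.08) = 12 × 0.4 = 4.8. Threshold = 1.96 × 4.8 = 9.41 points.
- Literal rule: P(change > 9.41) = P(Z > (9.41 + 12)/12) = P(Z > 1.784) = 3.7%, all of them worse.
- Improvement only: P(change < −9.41) = P(Z < (−9.41 + 12)/12) = P(Z < 0.216) = 58.6%.
- Absolute value: 3.7% + 58.6% = 62.3%.
- CSC: 0% as written. Under either repair, simulation gives about 32% if change is uncorrelated with baseline, rising to about 38% at a correlation of −0.7.

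**The case against.** The best defence is that this is a slip of notation. The wording around the rule speaks of the amount of change and of measurement error, neither of which is directional, and the cited method is standard. On that reading |RC| > 1.96 was meant and the cut-off crossing supplies the direction for CSC. A literal coding would also give 0% in both arms, which would be hard to miss, and code and output are to be made public. The outcome is the last of six secondary outcomes and feeds neither the primary SIAS model nor the other two primary outcomes.

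Much of this stands. A slip is the likeliest explanation, |RC| does repair CSC completely, and the primary analyses are untouched. Two things remain. The printed text contains neither an absolute value nor a reversed sign. And |RC| does not settle the reliable-change proportion, which the SAP also compares between arms: patients who reliably worsened would count as having achieved reliable change, so an arm with more deterioration would look better on it. The reference to the pilot research covers the criteria for CSC only and does not settle the direction of reliable change reported alone. In the illustration above the two readings differ by 3.7 percentage points, which is modest but was never prespecified.

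**Conclusion.** The concern holds. As written, the rule identifies only deterioration, and CSC is exactly 0% in both arms. That conclusion is algebraic and needs no assumption about SD, reliability, score range or treatment effect. The other percentages (3.7%, 58.6%, 62.3%, and 32% to 38% for CSC) depend on the assumed inputs and only show the order of magnitude.

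This is a wrong decision rule for a prespecified secondary outcome. It does not affect the primary comparisons. It should be corrected before analysis because the repair is nearly free and the choice between repairs should not be made with the data in hand.

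**What to change.** In the reliable-change section of the SAP:

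- Define reliable improvement as (SIAS pre − SIAS post) / √(2·SE²) > 1.96. Equivalently, keep the present numerator and require RC < −1.96.
- State that the RC condition in the CSC rule means reliable improvement.
- State that the between-arm test of reliable change uses reliable improvement. Report reliable deterioration (the same index below −1.96) as its own category by arm. The sign correction is necessary; reporting deterioration is a sensible addition that keeps worsened patients out of the success count.

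The cost is about one line of SAP text and one line of code. No extra data are needed, and the cut-off, the reliability estimate and the pooling method stay as they are.

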Trial Estimand and Missing Data

Estimand

In clinical trials, it is common that not all patients fully adhere to the prespecified treatment protocol (e.g., some patients may miss some treatment sessions). As a result, several different types of treatment effect can theoretically be estimated. These include the expected effect if all randomised participants had adhered or the treatment effect amongst only completers (among others, Mallinckrodt, Lin, Lipkovich, & Molenberghs, 2012). The *estimand* of an analysis refers to the type of conceptual effect that is being estimated (Mallinckrodt & Lipkovich, 2017). The present analyses will target the ‘de jure’ estimand,

which is the estimated treatment effect if all randomised individuals adhered to the treatment protocol. Mallinckrodt and Lipkovich (2017) recommend that analyses of the de jure estimand include (a) data from all randomised subjects, consistent with the intent-to-treat principle, and (b) all outcome data collected up to the point that a patient became non-adherent. In the present analyses, non-adherence will be defined as missing more than two consecutive treatment sessions. This means that analyses will utilise all data collected from all randomised subjects up until the point they became non-adherent (in contrast to a completer analysis, which uses data from only a subset of the randomised participants). Other estimands (e.g., de facto estimands) will be reported in subsequent papers. For more about estimands and their implications for data analysis, see Mallinckrodt et al. (2012).

Missing Data

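### The SIAS reliable-change rule never separates patients who reliably worsened, and no other planned outcome counts them

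*SAP*

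**What the plan says.** In the SAP section Reliable and Clinically Significant Change (SIAS), RC is post minus pre, divided by the square root of 2 × SE², with SE = SD_pre × √(1 − r) and r taken as McDonald's omega. If RC exceeds 1.96, "this indicates that the amount of change is greater than can be attributed to measurement error". For clinically significant change (CSC), "Individuals were required to have scored above a severity cut-off before treatment, achieved RC, and subsequently scored below the cut-off after treatment"; the cut-off is the midpoint of two published means, "which was 40.56 for the SIAS". The arms are then compared by a pooled test of proportions: "To determine whether the proportions of individuals achieving reliable and/or clinically significant change significantly differed between treatment arms".

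On the data set: "The analyses will examine the RC and CSC of the SIAS using the multiply-imputed datasets". The Estimand section targets the de jure effect, "which is the estimated treatment effect if all randomised individuals adhered to the treatment protocol", so that "analyses will utilise all data collected from all randomised subjects up until the point they became non-adherent". Non-adherence means missing more than two sessions in a row. De facto estimands are left to later papers. The Imputation Model section requires, as a minimum, the patient's earlier scores on the same variable.

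**The concern.** A reliable-change index has two tails. One holds patients who improved by more than measurement error, the other patients who worsened by more than that. The SAP uses one cut-off, describes it as an amount of change, and tests only achievement. Correcting the sign alone does not solve this, because the worsened then disappear among the unchanged.

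Nothing else planned for the first paper fills the gap. Diagnostic status cannot show worsening, since every patient has the diagnosis at baseline. The continuous outcomes are mean differences and clinician-rated severity is an odds ratio; these respond to worsening on average but do not count it. The paper could therefore report equal or better response in one arm without showing that more of its patients reliably deteriorated, although the per-patient RC values will already have been computed.

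The data set adds a smaller difficulty. An as-if-adherent imputed score may suit an efficacy contrast, but it does not describe what happened to a patient who was getting worse and left.

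**Working it through.** The SAP states no expected RC or CSC rate, SIAS SD, omega, correlation or dropout rate, so there is no figure to reproduce.

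**1. Direction.** RC > 1.96 with RC = (post − pre)/√(2·SE²) requires post > pre. CSC requires pre > 40.56 and post < 40.56, hence post < pre. The two cannot hold together, so CSC as written is impossible; among 1,000,000 random pairs on a 0-80 range, none qualified. The CSC rule also shows that higher scores mean greater severity, so RC as written flags deterioration.

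**2. Where a reliably worse patient goes under each reading.** For illustration, assume 48 per arm (the SAP gives at least 96 in total and no allocation ratio), 50% reliably improved in both arms, and 2% versus 15% reliably deteriorated (48 × 0.02 ≈ 1 and 48 × 0.15 ≈ 7 patients).

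| Reading of RC | Worsened patient is | RC rate, arm A vs arm B |
|---|---|---|
| As written (post − pre > 0) | achieving RC | 2% vs 15% |
| Absolute value | achieving RC | 52% vs 65% |
| Improvement only | pooled with unchanged | 50% vs 50% |

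Under the first two readings, the arm with more deterioration appears to have the higher rate of change. Under the third, the planned test sees no difference.

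**3. Size of a reliable rise.** Threshold = 1.96 × √2 × SD × √(1 − omega). With assumed SD 10-14 and omega 0.85-0.94:
- SD 10, omega 0.94: 2.772 × 10 × 0.245 = 6.8 points
- SD 12, omega 0.90: 2.772 × 12 × 0.316 = 10.5 points
- SD 14, omega 0.85: 2.772 × 14 × 0.387 = 15.0 points

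**4. What imputation does to leavers who had worsened.** Pre, last observed and one-month SIAS were simulated as trivariate normal in units of the pre-treatment SD (2,000,000 draws per scenario, 18 scenarios). Patients already reliably worse at the last observed visit were selected, and their one-month score was drawn given both earlier scores, as imputation under MAR would do. Assumed inputs:
- omega 0.85, 0.90 or 0.94
- correlations 0.6-0.7 (pre with last), 0.4-0.5 (pre with one month) and 0.5-0.8 (last with one month)
- mean change −0.2 or −0.3 SD at the last visit, with −0.8 or −1.2 SD respectively at one month
- one-month SD 1.2 times baseline

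Results across scenarios:
- imputed as reliably improved: 0-36%
- imputed as unchanged: 45-74%
- imputed as still reliably worse: 15-45%

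So 55-85% of this subgroup leaves the deteriorated category, mostly into unchanged. The improver share among all patients was 40-68%, so in these scenarios worsened leavers are not treated as typical responders. The draws show how such patients would be classified; they do not show that the classification is wrong, since some might truly have recovered had they adhered.

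**5. Precision of a direct count.** Exact (Clopper-Pearson) 95% limits with 48 per arm: for 0 events, the upper limit is 1 − 0.025^(1/48) = 7.4%; for 3 events (6.3%), the limits are 1.3% to 17.2%.

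**The case against.** The strongest reply is that this is an efficacy responder endpoint under a declared de jure estimand, that de facto estimands are deferred, and that harm monitoring normally sits in the protocol, which is not shown. That stands against any complaint about adverse-event reporting. It does not answer the present point: the SAP itself defines the RC classification in full, and that classification has no defined place for reliable worsening.

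A reader might infer that worsened leavers are largely turned into imputed improvers. The documents do not support this. Scores before non-adherence are kept and earlier scores must enter the imputation model, so recorded worsening pulls the imputed value upwards; improvers were never the majority in the calculations. Working from the average improvement alone would suggest a much larger effect, but it ignores those scores. It could apply only to leavers with no post-baseline SIAS (before week 4), whose SIAS record shows no worsening.

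Nor does RC rest only on imputed scores: adherent patients contribute their observed values. And it would be too strong to say that worsening must stay invisible. The SAP plans individual trajectory plots, trajectories by dropout status, reasons for discontinuation in the flow chart, a comparison of imputed with observed-data results, a delta-adjusted tipping-point analysis, and release of code and output. None of these counts deterioration, and the tipping-point analysis is framed as finding when significance is lost and is not tied to RC or CSC.

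The objection that a count would be imprecise is correct. It is a reason to show intervals, not to omit the count.

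**Conclusion.** The point holds for the classification. Under every reading of the rule, reliably deteriorated patients are either counted as achieving change or merged with the unchanged, and no other planned outcome counts them. This follows from the text and needs no assumption.

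The imputation point holds only in a limited form: leavers who had worsened are partly replaced by imputed unchanged or improved scores under MAR. The 15-45% still counted as worse, and the point thresholds of 6.8 to 15.0, depend on assumed SD, omega, correlations and mean changes; 48 per arm is also assumed.

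This is a completeness gap in one secondary outcome. The primary analyses are unaffected.

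**What to change.** - Define RC with an explicit direction, as pre minus post, so that RC > 1.96 means reliable improvement and RC < −1.96 means reliable deterioration.
- Classify each patient as reliably improved, no reliable change or reliably deteriorated, and report all three by arm at 1 and 6 months.
- Keep the responder and CSC analysis on the imputed data as planned.
- Add a descriptive count of reliable deterioration on observed scores by arm, including the last observed status of non-adherent patients and any later scores that exist (the SAP does not say whether they do). Give exact confidence intervals, because the usual standard error of a proportion is zero in an arm with no events.
- Do not summarise by the worst score over the five visits: for an unchanged patient with measurement error alone, that raises the chance of a false deterioration flag from 2.5% to about 9% (simulated with shared baseline error).

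The cost is SAP wording and one descriptive table. The RC values are already computed for the responder analysis and no extra visits are needed. The downsides are low precision and a data set that differs from the responder analysis, which a table footnote must state.
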